2.2 Definition of Study Dates

For each study subject,

- First dose date = the date on which the first dose of study drug is taken by the subject. If it is missing or incomplete, it is set to the earliest logically possible date on or after randomization.
- Last dose date = the date on which the last dose of study drug is taken by the subject. If it is missing or incomplete, it is set to the latest logically possible date recorded in diary.

2.3 Analysis Sets

Full Analysis Set (FAS)

The full analysis set includes all the randomized subjects who have received at least one dose of study drug (including placebo) according to the principle of intention-to-treat (ITT). Subjects will be analyzed as randomized.

Per Protocol Set (PPS)

The PP set is a subset of FAS, including subjects who do not have protocol deviations or events that will significantly affect efficacy assessments. Protocol deviations will be assessed and subjects who will be excluded from PPS will be identified and documented prior to database lock.

Safety Set (SS)

The safety set includes all randomized subjects who have received at least one dose of

the investigational product. Subjects in the Safety population will be analyzed as treated. The actual treatment arm will be defined by first drug dosing group. The SS will be used for analysis of laboratory examination data, adverse events, and adverse reactions.

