1.4.2 Phase II Study

The Phase II, dose range, and proof-of-concept study of HBM 9036 was completed in the US. This was a multicenter, randomized, double-blinded, placebo-controlled study. Subjects were randomly assigned to one of three treatment groups (HBM9036 Ophthalmic Solution 0.10%, 0.25% or placebo) to receive topical ophthalmic drops administered bilaterally BID. The study lasted for 8 weeks and included 6 visits. Although the primary sign of fluorescein staining at Visit 6 pre-CAE was not met with an ANCOVA analysis, analysis of the change in fluorescein staining score pre-CAE to post-CAE as well as post-CAE showed significant treatment differences from baseline starting as early as Visit 4 (Day 15) in total corneal and superior staining, and these significant treatment differences became consistent at Visit 5 (Day 29) and Visit 6 (Day 57). Significant improvements in burning and itching as assessed by the VAS were seen in favor of the HBM9036 0.25% group as early as Visit 4 (Day 15) and continued to Visit 6 (Day 57). Significant improvement was observed in total OSDI score in the HBM9036 0.25% treatment group compared with placebo group.

In the safety population, 44 (29.3%) subjects reported 64 AEs. Of them, 37 (24.7%) subjects reported 51 treatment-emergent adverse events (TEAEs), including 26 ocular TEAEs and 25 non-ocular TEAEs. All TEAEs were of mild or moderate severity. A total of 16 (10.7%) subjects reported at least one ocular TEAE related to the study drug. Of them 7 subjects were treated with HBM9036 (HL036) 0.10%, 8 subjects were treated with HBM9036 0.25%, and 1 subject was treated with placebo. The most common unexpected ocular TEAEs related to the study drug were installation site pain and allergic conjunctivitis. No deaths or SAEs were reported in the study. A total of 8 subjects withdrew from the study due to allergic conjunctivitis: 3 subjects were from HBM9036 (HL036) 0.10% group and 5 subjects were from HBM9036 (HL036) 0.25% group. No change of clinical significance was reported for other safety endpoints.

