9 STATISTICAL METHODS

9.1 Analysis Populations

The analysis populations in this study are defined as follows:

- **Full Analysis Set (FAS)** includes all the randomized subjects who have received at least one dose of study drug according to the principle of intention-to-treat (ITT). Subjects will be analyzed as randomized.
- **Per Protocol Set (PPS)** is a subset of the FAS population including all the subjects who do not have major protocol deviations and who complete the study. Subjects in the PP population will be analyzed as treated. Protocol deviations will be assessed before database lock and unblinding. For the subjects who have major protocol deviations (protocol violations), all their data should be eliminated from the PPS data, or the data of specific time points and/or subsequent time points should be eliminated.
- **Safety Set (SS)** includes all randomized subjects who have received at least one dose of the investigational product. The SS will be analyzed for all safety assessments. Subjects in the SS will be analyzed as treated.

In this study, the baseline data analysis will be based on the FAS. The efficacy analysis will be based on both FAS and PPS. The PPS will be used for main analysis. For the FAS, the missing data after dropout will be imputed using the Last Observation Carried Forward (LOCF) method. The observed and imputed data will be used for the analysis of FAS to assess the robustness of study results. The SS will be used for analysis of laboratory examination data, adverse events, and adverse reactions.

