9.5 Efficacy and Safety Analysis

9.5.1 Efficacy Analysis

9.5.1.1 Primary Efficacy Analyses

For primary efficacy endpoints, the pre- to post-CAE ICSS change will be calculated as post-CAE ICSS score-pre-CAE ICSS score. The change from baseline will be calculated as visit (post-CAE-pre-CAE)-baseline (post-CAE-pre-CAE) such that a positive difference indicates the change at study visit is larger than that at baseline. In addition, treatment comparisons between treatment and placebo groups will be calculated as treatment – placebo, such that a negative result indicates a better score for the treatment group (i.e., the treatment group have a smaller increase in dry eye signs or symptoms than the placebo group).

ANCOVA models will be used to compare the change from baseline in the pre- to post-CAE[®] inferior corneal fluorescein staining at Day 57 (Visit 6) (measured by the Ora Calibra[®] scale), between 0.25% HBM9036 Ophthalmic Solution and Placebo. The ANCOVA models will include the change in pre- to post-CAE ICSS at baseline as a covariate. The primary analysis will use LOCF imputation to have a full accounting of the FAS at the Day 57 visit, as described in Section 9.7.

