6.2.2 Analysis Methods

An ANCOVA model will be used to compare $\Delta\Delta$ ICSS at Day 57 (Visit 6) (measured by the Ora Calibra[®] scale), between HBM9036 and placebo. The ANCOVA model will include treatment and baseline Δ ICSS as the only 2 covariates. The between-group differences in $\Delta\Delta$ ICSS, two-sided 95% confidence intervals (CIs), and p-value will be reported.

Two-sample t-test will be conducted as a sensitivity analysis.

The primary analysis will be performed on the PP populations. After obtaining data sets and calculating changes from baseline, the following SAS code will be used to run the ANCOVA model on data sets:

```
PROC MIXED DATA = OUTDATA;  
  CLASS TREATMENT;  
  MODEL CHANGE_INFERIOR = BASELINE TREATMENT / SOLUTION COVB;  
  LSMEANS TREATMENT / CL PDIFF;  
  ODS OUTPUT LSMEANS = OUTLS DIFFS = OUTDIFFS;  
RUN;
```

where

- *TREATMENT* is the name of the treatment group variable
- *BASELINE* is the baseline post-CAE[®] – pre-CAE[®] inferior corneal staining score in the study eye
- *CHANGE_INFERIOR* is the post-CAE[®] – pre-CAE[®] inferior corneal staining score in the study eye at Visit 6 (Day 57 ± 3) – *BASELINE*

Sensitivity analyses will be performed:

- on the FAS population using the last observation carried forward (LOCF) - imputation method for missing values will be used which means the last value from the previous visits will be carried forward, matching pre-CAE[®] or post-CAE[®] time points and a pre-CAE[®] time point will never be imputed for a post-CAE[®] value, and vice versa to have a full accounting of the FAS at the Day 57
- on the FAS using MMRM methodology

An example of the SAS code implementation of the ANCOVA model for the FAS population using LOCF is as follows:

```
PROC MIXED;  
    CLASS TREATMENT;  
    MODEL CHANGE_INFERIOR = BASELINE TREATMENT / SOLUTION COVB;  
    LSMEANS TREATMENT / CL PDIFF;  
RUN;
```

For LOCF, baseline value will be used for post baseline if both visit 5 and visit 6 are missing.

An example of the SAS code implementation of the ANCOVA model for the MMRM is as follows:

```
PROC MIXED;  
    CLASS TREATMENT PTNO VISIT;  
    MODEL CHANGE_INFERIOR = BASELINE TREATMENT VISIT VISIT*BAELINE  
    VISIT*TREATMENT/ DDFM=KR SOLUTION CHISQ;  
    REPEATED VISIT/SUBJECT=PTNO TYPE=UN R RCORR;  
    LSMEANS TREATMENT*VISIT / PDIFF=ALL OM CL ALPHA=0.05 SLICE=VISIT;  
RUN;
```

where

- *PTNO* is Patient number (ID)
- *VISIT* is visit timepoint (5, 6)

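### SAP 2.3 lets undefined events remove subjects from the primary per-protocol set, which permits uneven selection on ocular reactions

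*SAP*

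**What the plan says.** Protocol 9.1 defines the PPS as the part of the full analysis set (FAS) "including all the subjects who do not have major protocol deviations and who complete the study". Deviations are to be assessed before both database lock and unblinding.

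SAP 2.3 defines it as the subset of the FAS "including subjects who do not have protocol deviations or events that will significantly affect efficacy assessments". The completion requirement is gone and *events* is new. The SAP does not define the term, list qualifying events, or say how they are judged. On process it says: "Protocol deviations will be assessed and subjects who will be excluded from PPS will be identified and documented prior to database lock". That sentence assesses deviations only, and it does not repeat the protocol's reference to unblinding.

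SAP 6.2.2 states: "The primary analysis will be performed on the PP populations". ANCOVA with LOCF and an MMRM, both on the FAS, are sensitivity analyses. The subgroup analyses (SAP 2.4) and the secondary comparisons (SAP 6.3) use the PPS, and no FAS version of them is named.

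The protocol disagrees with itself on which set is primary. Section 9.1 says "The PPS will be used for main analysis", while 9.5.1.1 says "The primary analysis will use LOCF imputation to have a full accounting of the FAS at the Day 57 visit".

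**The concern.** A PPS exclusion should rest on a departure from the protocol. An ocular reaction that changes the staining or redness score is not a departure. It may be a consequence of treatment. In the SAP's wording *events* stands beside deviations, so it must cover something that is not a deviation, and an adverse event in the measured eye is a natural candidate.

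Removing such subjects selects on something that happens after randomisation. If reactions are more frequent on active drug, a rule applied identically and under masking still removes more active subjects, because the imbalance lies in where the reactions occur. Deciding before database lock does not change that.

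The primary estimate feeds the Go, Pending or No-Go decision in SAP 1.4, whose two thresholds are only 0.2 apart. In the Pending region the SAP turns to other data such as secondary efficacy and safety, and the planned secondary comparisons rest on the same set.

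**Working it through.** **1. Whom do the added words affect?**

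| Subject | Protocol 9.1 PPS | SAP 2.3 PPS, primary ANCOVA |
|---|---|---|
| Major deviation affecting efficacy | out | out |
| Withdraws for a reaction before Visit 6 | out (non-completer) | no Visit 6 value, so not in the unimputed ANCOVA |
| Has a reaction, no deviation, supplies Visit 6 data | in | may be dropped as an event |

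The second row rests on Protocol Table 1, whose end-of-treatment column lists neither CAE exposure nor fluorescein staining. Only the third row depends on the wording.

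**2. How uneven were reactions before?** From Protocol 1.4.2:
- "A total of 8 subjects withdrew from the study due to allergic conjunctivitis": 3 on 0.10% and 5 on 0.25%, hence 8 - 3 - 5 = 0 on placebo.
- Subjects with a drug-related ocular treatment-emergent event: 8 on 0.25% and 1 on placebo.
- Safety population: 44/0.293 = about 150 in three groups. Arm sizes are not given, so I assume about 50 each. That gives 16% against 2% with a related ocular event (Fisher exact p about 0.03, and the same for arms of 45 to 55).

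If the 5 withdrawals on 0.25% are all among the 8 (overlap is not reported), 8 - 5 = 3 subjects had a related ocular event without withdrawing for allergic conjunctivitis.

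**3. Reproduce the plan's own figures.** SD 0.7 and 40 per arm (SAP 1.4). With benefit written as positive:
- SE = 0.7 x sqrt(2/40) = 0.1565
- P(Go) = 1 - Phi((0.3 - d)/SE)
- d = 0: 1 - Phi(1.917) = 2.8% (SAP Table 1: 3.0%)
- d = 0.1: 1 - Phi(1.278) = 10.1% (SAP Table 1: 9.9%)

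All 15 cells of the table agree within about 1 percentage point.

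**4. Illustration.** Assume 3 of 50 active subjects and no placebo subjects are dropped, and that the dropped subjects' staining change is h worse than that of the others in their arm. The difference moves toward benefit by (3/50) x h.
- h = 0.5: shift 0.03. h = 1.0: shift 0.06.
- P(Go) = 1 - Phi((0.3 - d - shift)/0.1565)

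| True difference d | No shift | Shift 0.03 | Shift 0.06 |
|---|---|---|---|
| 0 | 2.8% | 4.2% | 6.3% |
| 0.1 | 10.1% | 13.9% | 18.6% |

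**5. Sensitivity to the assumptions.**
- One placebo subject is also dropped, with the same h: net shift (3/50 - 1/50) x h = 0.02 to 0.04. Go becomes 3.7% to 4.8% at d = 0, and 12.5% to 15.3% at d = 0.1.
- The 3 are counted among 40 completers, not 50 randomised: shift (3/40) x h = 0.0375 to 0.075, with SE = 0.7 x sqrt(1/37 + 1/40) = 0.1597. Go becomes 5.0% to 7.9% at d = 0, and 15.4% to 21.7% at d = 0.1.
- h = 0: no shift, only fewer subjects.
- h negative: the sign reverses. A shift of -0.03 to -0.06 gives Go of 1.8% to 1.1% at d = 0.

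**The case against.** The strongest reply is that the US withdrawals do not bear on these words. A subject who leaves for allergic conjunctivitis has no Visit 6 staining and was already outside the protocol's PPS. A reader might infer that the SAP wording is what removes those subjects from the active arm. It is not; they are lost with or without it. This stands, and it is why the illustration uses about 3 subjects rather than 5 or 8.

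Second, the direction is not shown. The endpoint is the change from baseline in the post-CAE minus pre-CAE increment, on a scale that stops at 4. A reaction that raises pre-CAE staining could shrink the increment and make the subject look better. A reader might infer that the bias must favour the drug, but neither document reports staining change in subjects with reactions. Some related events may also have been instillation-site pain, for which no effect on staining is stated. This stands.

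Third, the SAP does not say that events means adverse events, and the rule covers both arms. A reader might infer that it directs removal of drug reactions in one arm. The text permits uneven removal but does not order it.

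Fourth, there are safeguards. The sponsor, CRO and sites are masked (SAP 1.5), exclusions are fixed before lock, reasons are listed (SAP 3.2), and the two FAS analyses would help expose a result driven by PPS exclusions. This stands in part. Masking does not remove selection on an outcome, and the FAS analyses cover the primary endpoint only and are labelled sensitivity.

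**Conclusion.** The concern holds as a defect of the rule. SAP 2.3 gives open discretion to exclude subjects from the primary analysis set for something that treatment may cause, where the protocol did not. Its reach is limited to subjects who react and still supply Visit 6 data.

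On the main illustration the estimate moves by 0.03 to 0.06, and the chance of a Go rises by about 1.5 to 3.5 percentage points at no effect and by about 4 to 8.5 points at a true difference of 0.1. That last value is the SAP's own boundary: it calls differences short of 0.1 of little relevance. These figures rest on an assumed count of dropped subjects, an assumed arm size in the US study, complete overlap between withdrawals and related events, and an assumed worse staining change. They show what the wording could do and are not an estimate of what it will do.

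The correction should be made. It is cheap, and the set feeds a Phase III decision and analyses that have no FAS counterpart.

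**What to change.** - Delete *or events* from SAP 2.3.
- Limit PPS exclusions to a closed list of protocol departures, for example an entry criterion not met, wrong treatment received, non-compliance, or no Visit 6 CAE assessment. Fix the list and the excluded subjects before database lock and unblinding.
- State that an adverse event, or its effect on the eye, is never by itself a reason for exclusion.
- In any non-compliance criterion, keep the exception in Protocol 6.7 for dosing reduced or interrupted because of adverse events. SAP 5.2.2 does not repeat it, so reactions could otherwise re-enter as deviations.
- Report the FAS result beside the PPS result, because subjects without a Visit 6 CAE remain outside the PPS.
- Reconcile Protocol 9.1 (PPS as the main analysis) with Protocol 9.5.1.1 (FAS with LOCF as primary).

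The cost is wording only, with no new data. The PPS estimate may be slightly noisier or less favourable.

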2.4 Definition of Subgroups

The four subgroups below are considered for subgroup analyses of primary efficacy outcome:

- Baseline pre-CAE[®] inferior corneal staining score $<2, \geq 2$;
- Baseline conjunctival redness score $<2, \geq 2$;
- Duration of dry eye disease ($<$ average level (year) \geq average level (year));
- Time to qualify during CAE[®] at Visit 2 (<20 minutes or ≥ 20 minutes)

The subgroup analyses above will be performed for secondary efficacy outcomes like pre to post-CAE[®] ICSS, pre-CAE[®] ODS, VAS(Burning) and Diary. To determine who get qualified study eye for ODS at Visit 2 within 20 minutes vs. after 20 minutes as defined by:

Reporting an Ocular Discomfort score ≥ 3 at 2 or more consecutive time points in at least the study eye during CAE[®] exposure (if a subject has an Ocular Discomfort rating of 3 at time = 0 for an eye, he/she must report an Ocular Discomfort rating of 4 for two consecutive measurements for that eye). Note: a subject cannot have an Ocular Discomfort score of 4 at time = 0).

Duration of dry eye disease will be defined by informed consent date (only year) – diagnosis date (only year). If diagnosis date is 2019, the duration will be 1. All subgroup analysis will base on study eye and PPS.

2.5 Study Day and Relative Day

Study Day 1 or Day 1 refers to the day of randomization [the start of the first study agent administration]. All efficacy and safety assessments at all visits will be assigned a day relative to this day.

Study day is defined as:

- Day on or after Day 1: Date – (date of Day 1) + 1;
- Day before Day 1: Date – (date of Day 1).

2.6 Baseline

Baseline measures are defined as the last non-missing measure prior to the initiation of study treatment, usually at Visit 2. If a measure is taken both pre-CAE[®] and post-CAE[®], the baseline will be the time point matched pair. For the non-CAE[®] Visit 3 and Visit 4, the baseline will be the pre-CAE[®] value. For changes from pre-CAE[®] to post-CAE[®], the baseline will be the last non-missing change from pre-CAE[®] to post-CAE[®] prior to initiation of study treatment at Visit 2. For measures from daily subject diaries, baseline is defined as the average of all days during the run-in period. For some safety endpoints like IOP, Fundus photography/Dilated fundoscopy and Slit-Lamp Biomicroscopy Examination, baseline will be the last non-missing measure prior to the initiation of run-in placebo, usually at Visit 1. For BCVA, baseline will be the last non-missing measure prior to the initiation of study treatment, usually at Visit 2. Change from baseline will be calculated as follow-up visit minus baseline value. In this study, the baseline data analysis will be based on the full analysis set (FAS).

3. Subject Disposition

3.1 Disposition

Subject disposition will be presented in terms of the numbers and percentages of subjects who were randomized, completed the study, and discontinued from the study. Disposition will be summarized by treatment group and for all subjects.

The number of randomized subjects in each of the analysis populations (FAS, PPS and SS) will be displayed by treatment. Percentages are based on the total number of subjects randomized in each treatment group.

The number and percentage of subjects prematurely discontinued from the study and the reasons for study discontinuation will be summarized by treatment group for all randomized subjects. The reasons for study discontinuation that will be summarized including: AE, subject choice, etc. A subject listing will be provided that includes the date of and reason for premature study discontinuation.

3.2 Protocol Deviations

The number and percentage of subjects with any protocol deviations will be summarized by treatment group for all randomized subjects. A subject listing will be provided that includes the date and description of each deviation. In addition, subject listings will be provided that include treatment, whether inclusion and exclusion criteria were met, and inclusion in the FAS, PPS, and SS populations. In addition, subjects who will be excluded

from PP will be identified prior to database lock. Reasons of exclusion will be provided in a listing.

4. Demographics and Baseline Characteristics

4.1 Demographics

The demographic variables collected in this study include age, sex, race, ethnicity and iris color. Demographic variables will be summarized, overall and by treatment group, for the FAS.

Age (years) will be summarized using continuous descriptive statistics. Age will also be categorized as follows: <65 years and ≥65 years. Age will be reported in years and calculated using the following formula:

Age = (informed consent date – date of birth) / 365.25 (take the floor value as an integer)

If the date of birth is partially missing for days in eCRF, 15th will be used for imputation.

Because the study is conducted in China. The vast majority of study subjects, if not all, is expected to be Chinese. Therefore, a summary of race and ethnics, as well as eye colors and other demographics that are almost no variation among Chinese will not be provided to streamline the study report. If there are non-Chinese subjects. Race/ethnics and other race/ethnics related demographics will be provided in a listing.

4.2 Baseline Disease Characteristics

Baseline disease characteristics will be summarized by treatment group using continuous descriptive statistics for pre-CAE[®] to post-CAE[®] Inferior Corneal Staining Score (ICSS), pre-CAE[®] Ora Calibra[®] Ocular Discomfort Scale (ODS), total OSDI[®] score, post-CAE[®] TFBUT, Ora Calibra[®] Ocular Discomfort and 4-Symptom Questionnaire, Ora Calibra[®] Conjunctival Redness Scale, unanesthetized Schirmer's test, Visual Analogue Scale (VAS), BCVA, IOP and others.

4.3 Medical History

Medical history will be coded using MedDRA Version 22.

Ocular medical history will be summarized using discrete summary statistics and presented by treatment group at the subject by System Organ Class (SOC) and Preferred Term (PT) using the FAS population. Non-ocular medical history will be similarly summarized at the subject. If a subject reported the same PT multiple times within the

same SOC, that PT will only be reported once within that SOC. Listings of medical history will be generated separately for ocular and non-ocular data.

5. Treatments and Medications

5.1 Prior and Concomitant Medications

Prior and Concomitant medications will be coded using WHO Drug Global Dictionary March 2019 and summarized to the therapeutic drug class according to Anatomical Therapeutic Chemical (ATC) 4 classification and preferred name. Prior medications are defined as any therapy used and stopped before the first day of run-in period. Concomitant medications are defined as any therapy used on or after the first day of run-in period, including those that started before and continue after the start of the first day of run-in period.

Prior and concomitant medications will be summarized separately using the FAS population. Ocular and non-ocular medications will be summarized separately. Medications will be tabulated for each treatment group using frequencies and percentages. Subjects may have more than one medication per ATC text. At each level of subject summarization, a subject will be counted once if he/she reports one or more medications. Percentages will be based on the number of subjects in each treatment group. Listings of concomitant medications will be generated separately for ocular and non-ocular data.

